Patients will be introduced to and asked to participate in the trial when they arrive to the surgical ward or emergency department by the surgical resident. They will not be subjected to any additional steps other than the standard hospital protocols as our trial begins in the operating room where patients will be randomly allocated into 2 groups: the control group (direct wound closure) and the intervention group (PVI wound wash before closure).

After the operation, patients will be monitored and observed at the hospital by the staff until discharge and will be given a specialized follow-up card. Following discharge, follow-up will be in the form of fixed outpatient clinic visit after the first week postoperatively and continue with phone calls made at regular 1-week intervals inquiring about symptoms and signs of SSI based on a questionnaire guided by the CDC definitions [27]. If a patient displays ≥ 1 symptom listed in the CDC checklist (See appendix 5), he/she will be invited to follow-up in our outpatient clinic and will be identified by their card. This will allow the physician to fill out the data collection form in their files and obtain a picture for documentation purposes. Follow-up will continue for a period of 30 days.

Sample Size

Using PASSII program for sample size calculation and assuming SSI incidence of 10% in control group and 5% in intervention group, setting **power** at 80% and **α -error** at 0.05, sample size of 345 patient for each group will be needed. We plan to enroll an additional 10% of the calculated sample size for each group in anticipation of a loss to follow-up rate of 10%. The total sample size will be **760 patients**.

Assignment of Interventions

Sequence Generation

A statistician not directly involved in the study or analysis will prepare a computer-generated randomization sequence. No blocking will be used. The sequence will be provided to the trialists in the form of serially numbered opaque envelopes containing details of either the intervention or the control and a random identifier.

Enrolment and Allocation Concealment

The patients will be enrolled by the resident doctors and given a study ID number.

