The allocation sequence will be made available to the OR head nurse in the form of sealed envelopes. The head nurse will provide the surgeons with closed opaque envelopes which will be opened by the nurse directly before wound closure. The head nurse will ensure that the envelopes are opened at wound closure and not before it. After the intervention/control is carried out, the random identifier will be noted down in the patient's operative data collection form. Following that, the nurse will tear the envelope and its contents.

Blinding

The patients and outcome assessors will be blinded. The details of which intervention was used will not be recorded in the regular patient records. The surgeons will be blinded till directly before wound closure, however, because of the nature of intervention, complete blinding of the surgeons would be impossible.

Data Collection Methods

Preoperative data collection will aim to collect baseline data about the recruited patients: patient identifiers, age, BMI, comorbidities including hypertension, diabetes, CKD, chronic liver disease, chronic heart failure, as well as any documented medication use and ASA score; through a standardized data collection form. All patients will be monitored by the doctors who will be responsible for filling their follow-up data till 30 days postoperatively (See appendix 6 for data collection forms).

Teams of four (surgeons or medical students) will be recruited to collect data from included surgical departments, each team collecting information over a two-week interval from all patients undergoing included surgical procedures in the department. Teams will then follow up with patients recruited in this allowed interval over the 30-day follow-up period, according to the methods described above.

We will obtain written informed consent from participants before surgery explaining the study procedures and the follow-up plans. All those who volunteer will be followed up in our clinics and provided carefree-of-cost.

Data Management

Package: R (latest available version)

Methods: Descriptive statistics will be presented as mean \pm SD for quantitative data. If the data is severely skewed/not normally distributed, median and IQR will be used. N & percentile will be used for qualitative data. Relevant statistical tests will be reported when applicable.

Statistical Methods

Suitable statistical tests will be used for data analysis.

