Involves only skin and subcutaneous tissue of the incision		
AND Patient has at least one of the following:		
a. Purulent drainage from the superficial incision.		
b. Organisms identified from an aseptically-obtained specimen from the superficial incision or subcutaneous tissue by a culture or non-culture based microbiologic testing method, which is performed for purposes of clinical diagnosis or treatment (for example, not Active Surveillance Culture/Testing (ASC/AST)).		
c. Superficial incision that is deliberately opened by a surgeon, physician* or physician designee AND Culture or non-culture based testing of the superficial incision or subcutaneous tissue is not performed AND Patient has at least one of the following signs or symptoms: 
 • Localized pain or tenderness • Localized swelling • Erythema • Heat 		
d. Diagnosis of a superficial incisional SSI by a physician* or physician designee.		
*The term physician for the purpose of application of the NHSN SSI criteria may be interpreted to mean a surgeon, infectious disease physician, emergency physician, other physician on the case, or physician's designee (nurse practitioner or physician's assistant).		
Comments:		
There are two specific types of superficial incisional SSIs:		

 1. Superficial Incisional Primary (SIP) – a superficial incisional SSI that is identified in the primary incision in a patient that has had an operation with one or more incisions (for example, C-section incision or chest incision for CBGB) 2. Superficial Incisional Secondary (SIS) – a superficial incisional SSI that is identified in the secondary incision in a patient that has had an operation with more than one incision (for example, donor site incision for CBGB) 		
Reporting Instructions for Superficial SSI:		
The following do not qualify as criteria for meeting the NHSN definition of superficial SSI:		

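### Local adverse events are recorded as effects of povidone-iodine, which a blinded assessor cannot judge and a control patient cannot have

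*Protocol*

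**What the plan says.** **Blinding.** The protocol states: "The patients and outcome assessors will be blinded". Of the operating team it says that "because of the nature of intervention, complete blinding of the surgeons would be impossible". Allocation is kept out of the regular records. Under Enrolment and Allocation Concealment, only a random identifier goes on the operative form, and the envelope is torn up after use.

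**Local adverse events.** Secondary outcome 6 (Outcomes) is local adverse events for povidone-iodine application, with local irritation and poor wound healing as the examples. Item 3-8 (Appendix 6, section 3) asks whether there was an adverse effect of applying it and offers local skin reaction, poor wound healing and other. The Monitoring section defines an adverse event as an occurrence probably caused by the intervention.

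**Who does follow-up.** On the ward, "patients will be monitored and observed at the hospital by the staff until discharge". In clinic, a symptomatic patient is seen again, and "This will allow the physician to fill out the data collection form in their files". Under Data Collection Methods, "All patients will be monitored by the doctors who will be responsible for filling their follow-up data till 30 days postoperatively". The same section adds "Teams of four (surgeons or medical students) will be recruited to collect data from included surgical departments" and "Teams will then follow up with patients recruited in this allowed interval over the 30-day follow-up period".

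**What counts as superficial SSI.** Criterion d in Appendix 5 is "Diagnosis of a superficial incisional SSI by a physician* or physician designee". Its footnote counts a surgeon as a physician.

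**The concern.** The outcome, the form item and the adverse-event definition all carry a causal attribution to povidone-iodine. The person completing the form is meant not to know whether it was used, and half of the patients will not have received it. A comparison of local wound events between arms needs the same event recorded by the same rule in both. Irritation and poor healing can occur after any operation, so the rate after direct closure is the background against which the washed arm has to be read. If the rule removes that background from the control arm, secondary outcome 6 has no comparator.

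A lesser question concerns the primary outcome. The blinding of assessors is promised, but the groups named for follow-up are described broadly enough to include someone who saw the closure, and criterion d rests on a diagnosis.

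**Working it through.** **Item 3-8: three ways to complete it**

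No figure in the protocol bears on this, so the reasoning is symbolic. Let b be the true rate of local wound events, equal in both arms (povidone-iodine does no local harm). Evaluable patients per arm, from Sample Size: 760 × 0.9 / 2 = 342. A valid record shows about 342b events in each arm.

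1. *Item read as plain observation.* Every reaction or healing problem is ticked, whatever its cause. Expected record: 342b against 342b. The comparison is valid, but this departs from the item's wording and from the Monitoring definition.
2. *Item read literally, arm known when attribution is made.* A control patient received no povidone-iodine and so cannot have an effect of it. Control arm: 0. Washed arm: 342bq, where q is the share of events attributed to the wash. The recorded difference is bq − 0 = bq, a spurious excess although povidone-iodine did nothing.
3. *Item read literally, assessor blinded.* The assessor guesses or leaves the item blank. If a share q is ticked regardless of arm, the record is 342bq against 342bq. This is not biased between arms, but a share 1 − q of events is lost and q depends on the individual assessor.

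The protocol does not say which reading applies. With several teams each collecting data over a two-week interval, the readings can be mixed and the total has no clear meaning. In the copy at hand the item also shows no 'none' option, so a blank could mean no event or not assessed. Text extraction may have altered the form, so this last point is tentative.

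**SSI classification: how much could be at stake**

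The documents do not say how many SSIs would rest on criterion d or who would judge them. The following inputs are assumptions, with a true SSI rate of 10% in both arms and 342 per arm:

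- s, share of SSIs that rest on judgement: 0.2 to 0.6
- u, share of those judged by someone who knows the arm: 0.25 to 0.5
- k, share of those left unlabelled in the washed arm: 0.1 to 0.3

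Recorded rate in the washed arm = 10% × (1 − s·u·k). The rejection probability is that of the two-sided pooled z-test at 0.05, summed exactly over both binomial distributions.

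| s, u, k | s·u·k | Recorded rate | SSIs lost of about 34 | Rejection, two-sided | In favour of povidone-iodine |
|---|---|---|---|---|---|
| none | 0 | 10% | 0 | 4.95% | 2.47% |
| 0.2, 0.25, 0.1 | 0.005 | 9.95% | 0.2 | 4.95% | 2.60% |
| 0.4, 0.375, 0.2 | 0.03 | 9.7% | 1.0 | 5.14% | 3.33% |
| 0.6, 0.5, 0.3 | 0.09 | 9.1% | 3.1 | 6.76% | 5.86% |

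At the midpoints the two-sided false-positive rate hardly moves. The extreme row needs all three assumptions at their limits and in the same direction.

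**The case against.** *On item 3-8.* The tick-box options are observable in any patient, the form does not confine the item to one arm, and a sensible assessor will record what is seen. The item does not reveal the arm, and it concerns a secondary outcome. All of this stands and limits the weight of the point. It does not answer it: a valid comparison then depends on assessors departing from the item's wording and from the protocol's definition. Analysis cannot recover control-arm events that were never written down.

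*On SSI.* A reader might infer that operating surgeons will judge SSI in their own patients. The protocol does not say so. It requires blinded assessors and treats surgeons separately; read normally, a person who saw the closure is not blinded and so may not assess. The groups named for follow-up are generic, and the teams are recruited to collect data, not to operate. Patients are blinded, the symptom survey is fixed, clinic review includes a photograph, and Appendix 5 says cellulitis alone does not satisfy criterion d. What remains is that the rule is stated without being put into operation.

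A reader might also infer that a few relabelled SSIs could decide the trial: at the planned rates 34 against 17 gives p = 0.013, and 34 against 21 gives p = 0.068. That is the ordinary fragility of such counts and is not specific to blinding. Recording 21 true events as 17 means losing 4/21 = 19%, whereas the most extreme assumptions above lose 9%.

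**Conclusion.** The point holds for local adverse events. As worded, item 3-8 and the adverse-event definition cannot be applied by a blinded assessor, and read literally they give the control arm no events at all. Secondary outcome 6 then has no sound comparison between arms. The conclusion follows from the wording alone. Its numerical effect cannot be derived, because the documents give no background rate of local wound events and do not say how assessors will read the item.

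For SSI only a minor clarification is warranted. The documents do not place operating surgeons in the assessor role, and neither the size nor the direction of any bias can be derived from them. On assumed inputs the false-positive rate goes from 4.95% to 5.1% at the midpoints and 6.8% at the extreme.

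**What to change.** **Main change.** Reword item 3-8 to ask about any local skin reaction or poor wound healing, with an explicit 'none' option. Complete it for every patient in both arms whatever the presumed cause, and compare by arm at analysis. Word secondary outcome 6 to match. Where the Monitoring definition calls for attribution to povidone-iodine, someone other than the SSI assessor makes it, as a separate step. The cost is one reworded form item, a matching line in Outcomes, and slightly more events recorded.

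**Minor clarification.** Add to Blinding that a person present at a patient's wound closure neither classifies that patient's SSI nor supplies the diagnosis counted under criterion d for the trial outcome. Covering the diagnosis as well as the form matters, because otherwise a surgeon's diagnosis on the ward could be carried onto the form. This governs only what counts for the trial and leaves clinical care unchanged. It costs a sentence and some division of roles within the teams; the documents give no staffing figures from which to judge that burden.

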The study participants will be divided into 4 groups (Clean, Clean-contaminate, Contaminated, Dirty).

Each group will be stratified and analyzed separately.

Subgroup analyses will also be performed according to the type of surgical access (open versus minimally invasive), and the presence or absence of Diabetes.

The need for additional subgroup analyses will be determined at the time of completion of data collection.

Both per-protocol and intention to treat analyses will be used and their findings will be reported.

Monitoring

The study will not employ a data monitoring committee (DMC) as the trial is conducted on an adult population with no perceived risk to either arm of the trial.

Interim analysis will be done on reaching 50% of the total sample size by an independent statistician blinded for the intervention allocation. The unblinded data will be reported to the Ain Shams Surgical Research Group. The primary purpose of this analysis would be to determine if the study should be prematurely terminated in the case of patient harm. The final decision on the matter will reside with the Ain Shams Surgical Research Group and the study's principal investigators.

In our study an adverse event will be defined as any medical occurrence in a subject with a probable causal relation to the intervention.

Adverse events will be collected after the subject has provided consent and enrolled in the study.

The known as well as novel adverse effects of the study intervention (povidone iodine) will be investigated and recorded until the period of patient follow up is completed.

Ethics and Dissemination

Ethical Approval

This protocol, the template informed consent forms (Arabic and English versions), and any subsequent modifications will be reviewed and approved by the applicable IRB [institutional review board] with respect to scientific content and compliance with applicable research and human subjects' regulations prior to starting the study.

Protocol Amendments

Any modifications to the protocol which may impact on the conduct of the study, potential benefit of the patient or may affect patient safety, including changes of study objectives, study design, patient population, sample sizes, study procedures, or significant administrative aspects will require a formal amendment to the protocol. Such amendments will be reviewed and approved by the IRB prior to implementation in accordance with local regulations.

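### Statistical Methods commits to separate analyses in four wound classes without calling them subgroups or saying that the class-combined comparison, which the trial is sized for, answers the objective

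*Protocol*

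**What the plan says.** Study Objective gives one aim, the efficacy of the wash in preventing surgical site infection (SSI). Trial Design is two-arm superiority with 1:1 allocation. The primary outcome, superficial and deep SSI within 30 days, is not divided by wound class. Sample Size rests on one pair of rates, "assuming SSI incidence of 10% in control group and 5% in intervention group", and concludes that a "sample size of 345 patient for each group will be needed".

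Statistical Methods opens with "Suitable statistical tests will be used for data analysis". Its first specific rule is "The study participants will be divided into 4 groups (Clean, Clean-contaminate, Contaminated, Dirty"), followed by "Each group will be stratified and analyzed separately". The next sentence begins "Subgroup analyses will also be performed according to the type of surgical access" and adds diabetes. Further subgroups may be chosen once data collection is complete. The section ends with "Both per-protocol and intention to treat analyses will be used and their findings will be reported".

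**The concern.** The design, outcome and sizing all point to a single comparison across all patients. The one concrete analysis rule for comparing the arms points to four comparisons within wound classes. Nothing in Statistical Methods combines the classes, calls the class analyses subgroups, or says which result answers the objective. The term subgroup is used for access, diabetes and possible later additions; for wound class the text says only that the groups are analysed separately.

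The stakes depend on the meaning:

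- **Class analyses as the main analysis.** Each would have much less power than planned, and one objective could receive four different answers.
- **Class analyses as subgroups.** The overall comparison is untouched. Two weaknesses remain: the answering result is not fixed in advance, and four separate tests do not show whether the effect differs between classes.

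**Working it through.** **Inputs.** From Sample Size: 10% and 5%, power 80%, α 0.05 (sidedness not stated), 345 per arm, 10% added for loss, 760 in total. From Statistical Methods: four wound classes. Class shares and class-specific SSI rates are not in the protocol, so they are assumed below.

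**The plan's own figure.** Two-proportion z test with pooled variance: n = [z_α√(2p̄q̄) + z_β√(p₁q₁ + p₂q₂)]² / (p₁ − p₂)².

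- p̄ = 0.075, so √(2 × 0.075 × 0.925) = √0.13875 = 0.3725.
- √(0.10 × 0.90 + 0.05 × 0.95) = √0.1375 = 0.3708.
- One-sided: (1.645 × 0.3725 + 0.842 × 0.3708)² / 0.0025, which rounds up to 343.
- Two-sided: (1.96 × 0.3725 + 0.842 × 0.3708)² / 0.0025, which rounds up to 435.
- 345 × 1.10 = 379.5, rounded to 380 per arm, or 760.

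So 345 is the size of one whole-trial comparison (at one-sided 0.05), not of four.

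**Power within a class, 10% vs 5%.** Power = Φ{[(p₁ − p₂)√n − z_α√(2p̄q̄)] / √(p₁q₁ + p₂q₂)}. For equal quarters n = 345/4 = 86.25 and 0.05 × √86.25 = 0.4644. Two-sided: (0.4644 − 0.7301)/0.3708 = −0.717, giving 23.7%. One-sided: (0.4644 − 0.6127)/0.3708 = −0.400, giving 34.5%.

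| Share of patients in the class | n per arm | Two-sided | One-sided |
|---|---|---|---|
| 10% | 34.5 | 12.0% | 19.5% |
| 25% | 86.25 | 23.7% | 34.5% |
| 60% | 207 | 48.8% | 61.3% |
| 70% | 241.5 | 55.0% | 67.1% |
| All patients | 345 | 70.4% | 80.3% |

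**Power within an equal quarter, rate halved, other control rates.**

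| Control rate | Two-sided | One-sided |
|---|---|---|
| 2% | 7.8% | 13.4% |
| 5% | 13.6% | 21.7% |
| 20% | 45.1% | 57.8% |
| 30% | 65.7% | 76.6% |
| 40% | 82.3% | 89.5% |

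The normal approximation is rough at low rates. An exact binomial calculation of the same test at 86 per arm, 5% vs 2.5%, gives 11.8% (24.4% one-sided).

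**Precision at 10% vs 5%.** The 95% half-width of the risk difference is 1.96 × √(0.1375/n): 7.8 points at n = 86 and 3.9 points at n = 345.

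**Why separate tests do not show a difference between classes.** Suppose the effect is the same, 10% vs 5%, in four equal classes, each with two-sided power 0.237. The chance that none is significant is 0.763⁴ = 0.339, and that all four are is 0.237⁴ = 0.003. A mixed picture therefore arises with probability 1 − 0.339 − 0.003 = 0.66, although nothing differs between classes.

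**The case against.** The ordinary reading is benign. The word *also* in the sentence on surgical access suggests that wound class is simply the first subgroup in a list. The sentence on per-protocol and intention-to-treat analyses is not limited to classes, and intention to treat suggests a whole-trial comparison. The last paragraph of Background states the comparison of the two arms as the aim. The test, the estimator and the interaction terms may sit in a statistical analysis plan that is not at hand.

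Most of this stands. A reader might infer that the protocol nowhere states the overall comparison, that the class analyses are the primary analysis, or that the trial is therefore underpowered. The documents support none of these. The overall comparison is visible in the aim, the design, the undivided outcome and the sizing. No sentence ranks the class analyses first, rules out combining them, or says that they replace the overall result.

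What survives does not depend on an unnamed test. It concerns a method that the protocol does state: separate analysis of each class, with no role assigned. Intention to treat and per-protocol define who is counted, can each be applied within a class, and are not ranked. An analysis plan that made the overall comparison primary would have to add to the one rule written down.

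It is also fair that the power figures rest on assumed shares and rates. A uniform 10% control rate across clean and dirty wounds is unlikely, and a class with a high rate could reach the planned power.

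**Conclusion.** The point holds as a rule that is badly fixed, not as an outright contradiction, and it should be corrected. Confidence is moderate because its weight depends on the intended meaning.

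On the likelier reading, with classes as subgroups, no power is lost for the overall comparison. What remains is that the answering result is not named and that separate tests are a weak basis for claims about individual classes. On the literal reading, with classes as the main analysis, power in an equal quarter falls from 70% to 24% two-sided (80% to 34% one-sided) at 10% vs 5%. The two-sided range is about 8% to 82% for a halved rate at control rates of 2% to 40%. At 10% vs 5%, no class holding up to 70% of patients reaches 80% power. These figures assume the class shares and rates shown and apply only on that reading.

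That 345 corresponds to a one-sided α is a separate issue; both versions are given so that this point does not depend on it.

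**What to change.** Replace the sentence that has each class analysed separately with text such as:

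> The primary analysis is one intention-to-treat comparison of 30-day SSI between arms in all randomised patients, stratified by wound class (for example Cochran-Mantel-Haenszel with a stratified risk difference and 95% CI). Wound class, surgical access and diabetes are subgroup analyses, each reported with a treatment-by-subgroup interaction test and per-level estimates with CIs.

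The named method is an example; what matters is one named comparison, in one named population, with wound class as a stratification factor. The results by class are still reported.

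Wound class should be recorded before the envelope is opened. It is already a field on the operative form (Appendix 6), but the protocol does not say when it is filled in. Under Enrolment and Allocation Concealment, "the random identifier will be noted down in the patient's operative data collection form" only after the intervention or control has been carried out, and by then the surgeon knows the arm. A stratification factor should not be open to that knowledge.

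The cost is one replaced sentence and one instruction on timing. The sample size stays the same and no new data item is needed. The downside is that no confirmatory claim can be made within a single wound class, and the interaction tests will have low power.

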Administrative changes of the protocol are minor corrections and/or clarifications that have no effect on the way the study is to be conducted will be agreed upon by the principal investigators and documented.

Informed Consent and Participant Rights

Surgical residents will introduce and discuss the trial to patients answering all questions and/or concerns they might have. Patients will then be able to have an informed discussion with the participating consultant. Surgical residents will then obtain written consent from patients willing to participate in the trial. Consent forms are provided for all patients involved in the trial in Arabic or English language.

The informed consent will be a tiered consent. Participants will be given the option to consent for the use of their data in current protocols or for future ancillary research unrelated to the clinical condition under study as well.

All participants will also be given a special follow up card. Any complications, if present, will be treated at the Ain Shams University Hospitals at no additional cost.

Healthcare-Information Security and Privacy

All study-related information will be stored securely at the study site. All participant information will be stored in locked file cabinets in areas with limited access. All data collection, process, and administrative forms will be identified by a coded ID [identification] number only to maintain participant confidentiality. All records that contain names or other personal identifiers, such as locator forms and informed consent forms, will be stored separately from study records identified by code number. All local databases will be secured with password-protected access systems. Forms, lists, logbooks, appointment books, and any other listings that link participant ID numbers to other identifying information will be stored in a separate, locked file in an area with limited access.

The Ain Shams Surgical Research Group will oversee the data storing process. All Principal Investigators will be given access to the cleaned data sets. All data sets will be password protected. To ensure confidentiality, data dispersed to project team members will be blinded of any identifying participant information.

Conflicts of Interest

All principal and team investigators declare no conflict of interest.

Publication Policy

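### With no DMC, unblinded interim data go to the group that runs the trial, and the protocol does not limit who may see or pass on the results while recruitment continues

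*Protocol*

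**What the plan says.** The Monitoring section dispenses with a DMC, on the ground that the patients are adults and neither arm is thought to carry risk. An interim analysis takes place "on reaching 50% of the total sample size by an independent statistician blinded for the intervention allocation". The next sentence reads "The unblinded data will be reported to the Ain Shams Surgical Research Group". The main stated purpose is to decide whether to stop early because patients are being harmed. "The final decision on the matter will reside with the Ain Shams Surgical Research Group and the study's principal investigators".

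Other sections bear on who may know what:

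- Under Participant Timeline, recruitment runs until the sample size is reached. No pause at the interim is mentioned.
- Under Blinding, patients and outcome assessors are blinded, the treatment given is kept out of the regular records, and surgeons learn it only just before closure.
- Under Healthcare-Information Security and Privacy, the Group oversees data storage and the principal investigators receive the cleaned data sets. The one stated limit on data handed to the team is this: "To ensure confidentiality, data dispersed to project team members will be blinded of any identifying participant information".
- Under Publication Policy, the Group chooses the journal and must approve every paper and abstract.

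**The concern.** The arrangement is the reverse of the usual one. The person who is independent of the trial is masked, while the body that runs it and shares the decision to continue receives the unblinded data. The protocol states this as a choice, so it is not a detail left to a statistical analysis plan.

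What is at stake is the second part of the trial. The SSI criteria in Appendix 5 include a physician's diagnosis as one way of meeting the superficial definition, so the primary endpoint contains judgement. Follow-up teams may include surgeons (Data Collection Methods). If interim results reached people who recruit or assess, they could colour those judgements. Those who lead the trial could also be influenced in day-to-day decisions on conduct. Once the results have been seen, this cannot be undone.

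**Working it through.** **Inputs.** From Sample Size: 345 per group, 10% added for loss to follow-up, total 760, SSI rates of 10% (control) and 5% (intervention). From Trial Design: 1:1 allocation. From Monitoring: interim at 50% of the total. From Participant Timeline: 30 days of follow-up.

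**Step 1: reproduce the total.** 345 × 1.10 = 379.5, rounded up to 380 per group; 2 × 380 = 760. This matches the protocol.

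**Step 2: patients still to come.** 0.50 × 760 = 380 enrolled at the interim; 760 − 380 = 380 remaining.

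**Step 3: SSIs that could be known by arm.** Expected at the end with 345 evaluable per group: 345 × 0.10 + 345 × 0.05 = 34.5 + 17.25 = 51.75. At halfway: 17.25 + 8.625 = 25.9, so about 17 control and 9 intervention. As a cross-check, 190 per arm with 10% lost leaves 171 per arm: 17.1 + 8.55 = 25.7. With no loss at all the figure would be 19 + 9.5 = 28.5.

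**Step 4: the two figures are separate upper values.** If the interim falls exactly when 380 are enrolled, the latest patients are still within their 30 days and fewer than 26 SSIs are known. If it waits until 380 have completed follow-up, recruitment goes on meanwhile and fewer than 380 remain. The protocol gives no accrual rate, so the number remaining cannot be pinned down. Step 3 also applies only if the report shows SSI by arm, which the protocol does not say.

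**Step 5: who is shielded from what.**

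| Party | Stated position |
|---|---|
| Patients, outcome assessors | Blinded to treatment |
| Independent statistician | Blinded to allocation at the interim |
| Research Group | Receives the unblinded data |
| Principal investigators | Share the decision; have the cleaned data sets, with no limit stated on timing or allocation |
| Project team | Shielded from participant identity |

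No row, and no other sentence of the protocol, restricts the interim results themselves or their onward circulation.

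**The case against.** The case on the other side is substantial, and much of it stands.

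- *Someone must look at unblinded data to detect harm, and a full DMC may be out of proportion.* Agreed. The remedy below needs no DMC and keeps the harm review.
- *Interim knowledge does not reveal the next allocation.* This stands: envelopes are sealed and opaque, opened at closure, and there is no blocking.
- *Formal changes are controlled.* This stands too: "Such amendments will be reviewed and approved by the IRB prior to implementation in accordance with local regulations".
- *The late choice of subgroups is a weak example.* The protocol says "The need for additional subgroup analyses will be determined at the time of completion of data collection", but that freedom exists with or without an interim look, so it adds little here.
- *A narrower remedy would do:* leave the Group as recipient, restrict circulation, and bar recipients from recruiting or assessing. That would protect recruitment and assessment, but those who run the trial would still know the comparison.

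A reader might also infer more than the text supports:

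- *That a blinded statistician and unblinded data contradict each other.* They do not if the analysis is done on coded arms that are decoded afterwards, although the protocol does not say who decodes.
- *That participant identity is the only thing protected.* The Blinding section protects patients and assessors as well. What is missing is protection of the interim results.
- *That assessor blinding is broken.* This would need a patient-level report, patients still within 30 days of surgery, and recipients who assess outcomes or inform those who do. The protocol does not say that Group members recruit or assess.
- *That the type I error rate is inflated.* The stated main purpose is harm, and no efficacy stopping rule is given.

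**Conclusion.** The point holds as an unprotected route to bias. Followed as written, the plan gives comparative data in mid-trial to the Group that decides on continuation with the principal investigators, and nothing stops those data from going further. It is not a documented breach, and the size of any bias cannot be computed from the protocol.

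Only the exposure can be bounded: up to 380 of 760 patients still to come and, at the design rates with the planned loss, at most about 26 SSIs known by arm. This rests on three assumptions: that the report shows SSI by arm, that the design rates hold, and that no rule outside the protocol restricts circulation. Any separate analysis plan was not available. The change is a cheap improvement that should be made before the interim.

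**What to change.** Replace the sentence that sends unblinded data to the Group with text to this effect:

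1. The independent statistician prepares the arm-level comparison against a harm criterion that the sponsor writes beforehand, and reports only *continue* or *criterion met* to the Group and the principal investigators.
2. Arm-level data are released, only to the people needed for the harm decision, if the criterion is met or an unexpected safety concern is flagged.
3. Anyone who has seen unblinded interim data does not recruit patients or assess SSI while the trial continues, and does not pass the results on.

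The content of the harm criterion is for the sponsor to decide. The route for unexpected concerns in item 2 is needed because a criterion fixed in advance may miss new effects, and the Monitoring section covers these: "The known as well as novel adverse effects of the study intervention (povidone iodine) will be investigated and recorded".

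The cost is a few sentences and no new body, since the statistician is already planned. There are three drawbacks. The statistician loses the masking that the protocol now gives. Clinicians see arm-level data only on release. If data are released and the trial goes on, those who saw them can no longer recruit or assess SSI.
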